5.2. Study Participants

All participants who provided informed consent will be accounted for in this study.

The number of participants screened, screen failed, randomized, and re-randomized will be presented and grouped by treatment group. The number and percentage of participants who completed the study or discontinued treatment (along with reasons) and subsequently discontinued from the study (along with reasons) will be summarized. By-participant listing of the reasons for screen failure will also be produced. The number and percentage of participants in each analysis set will be tabulated, and a by-participant listing will be provided. The number and percentage of participants not meeting inclusion or exclusion criterion will be summarized and listed. The by-participant data listings of randomization information and consent status will also be provided.

If applicable, the impact of coronavirus disease 2019 on the study disposition will also be summarized and listed.

5.3. Primary Endpoints Analyses

The primary efficacy endpoint analysis will be performed based on the FAS. The PPS will also be used as a supplementary analysis of the primary endpoint. A sensitivity analysis will be performed by implementing participant-level imputation using the FAS. The supplementary analysis based on a logistic regression model will be additionally performed using the FAS. The primary endpoint analysis will be performed at the first analysis (Week 8).

The details of the statistical analyses of the primary endpoint are provided in the following sections and in Table 1.

5.3.1. Primary Endpoint

The primary endpoint is the proportion of participants with an MG-ADL total score reduction of ≥ 2 points from the Baseline in any 4 consecutive weeks during the first 8 weeks and who did not receive rescue therapy. To compute this, change from Baseline in the MG-ADL total score at each post-Baseline Visit of the first 8 weeks will be derived, where baseline is defined as the last nonmissing assessment prior to the first dose of study intervention. In general, this baseline assessment will be the Day 1 assessment. If the Day 1 assessment is missing, the latest observation during the Screening Period, where available, will be used as the baseline assessment.

Participants who discontinued early without achieving an MG-ADL total score reduction of ≥ 2 points from the Baseline in any 4 consecutive weeks during the first 8 weeks will be considered as nonresponders. Participants who received rescue therapy anytime during the first 8 weeks will be considered as nonresponders.

5.3.2. Main Analytical Approach

5.3.2.1. Primary Analysis for the Primary Endpoint

The differences in proportions, along with 2-sided 90% confidence intervals (CIs) using Chan and Zhang method (Chan, 1999), will be presented between the ALXN2050 180 mg bid group and the placebo group. P-value using the Barnard's unconditional exact test to determine whether there is a difference in the proportions of responders between the 2 treatment groups will be presented. No imputation will be implemented.

5.3.2.2. Secondary Analysis for the Primary Endpoint

The differences in proportions, along with 2-sided 90% CIs using Chan and Zhang method (Chan, 1999), will be presented for the following pairwise comparisons: between the ALXN2050 120 mg bid group and the placebo group and between the ALXN2050 180 mg bid group and the ALXN2050 120 mg bid group.

In addition, the proportions of responders in each treatment group will be presented, along with exact 2-sided 90% CIs using the Clopper-Pearson method.

A trend analysis to detect whether there is an increasing trend in the proportions of responders in the primary endpoint will be presented, along with the p-value using the Cochran-Armitage test. No imputation will be implemented.

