## 9.2. Sample Size Determination

The study has 3 treatment groups: ALXN2050 180 mg bid, ALXN2050 120 mg bid, and placebo. The goals of this study are to establish proof of concept for the treatment of gMG with ALXN2050 and to select a dosage for further development of ALXN2050 in gMG. Both trend analysis among the 3 treatment groups and differences in proportions of responders between the ALXN2050 180 mg bid group and the placebo group in the primary endpoint are used for sample size determination.

Data from the Argenx ADAPT study and the Momenta Vivacity-MG study were used to estimate the response rate on placebo with background standard-of-care treatment. Based on the data from both studies, the response rate for the placebo group is assumed to be 25%. A sample size of 54 evaluable participants with a randomization ratio of 1:1 to the placebo group and the ALXN2050 180 mg bid group results in approximately 80% power to detect a treatment effect (difference in the proportions of responders) of 35% between the 2 treatment groups, using a 2-sided type I error rate of 0.1 and the exact binomial computation method. An additional 13 evaluable participants will be enrolled to the ALXN2050 120 mg bid group, for a total of 67 evaluable participants.

Assuming that the response rate for the ALXN2050 120 mg bid group is 45%, with a total of 67 evaluable participants, the study has approximately 80% power to detect the increasing trend in the proportions of responders, using Cochran Armitage test at a 2-sided type I error rate of 0.1.

Assuming about 5% non-evaluability, the study is planned to enroll 70 participants in total.

The sample size calculations were performed in PASS 2020.

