## 9.4.6.1.2. Secondary Analysis for the Primary Endpoint

The differences in proportions, along with 2-sided 90% CIs using Chan and Zhang method (Chan, 1999), will be presented for the following pairwise comparisons: between the ALXN2050 120 mg bid group and the placebo group, and between the ALXN2050 180 mg bid group and the ALXN2050 120 mg bid group.

In addition, the proportions of responders in each treatment group will be presented along with exact 2-sided 90% CIs using the Clopper-Pearson method.

Trend analysis to detect whether there is an increasing trend in the proportions of responders in the primary endpoint will be presented along with the p-value using Cochran Armitage test.

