3. SAMPLE SIZE DETERMINATION

The study has 3 treatment groups: ALXN2050 180 mg bid, ALXN2050 120 mg bid, and placebo. The goals of this study are to establish proof of concept for the treatment of gMG with ALXN2050 and to select a dosage for further development of ALXN2050 in gMG. For sample size determination, both trend analyses among the 3 treatment groups and differences in proportions of responders between the ALXN2050 180 mg bid group and the placebo group in the primary endpoint are used.

Data from the Argenx ADAPT study and the Momenta Vivacity-MG study were used to estimate the response rate on placebo with background standard-of-care treatment. Based on the data from both studies, the response rate for the placebo group is assumed to be 25%. A sample size of 54 evaluable participants with a randomization ratio of 1:1 to the placebo group and the ALXN2050 180 mg bid group results in approximately 80% power to detect a treatment effect (difference in the proportions of responders) of 35% between the 2 treatment groups, using a 2-sided type I error rate of 0.1 and the exact binomial computation method. An additional 13 evaluable participants will be enrolled to the ALXN2050 120 mg bid group for a total of 67 evaluable participants.

Assuming that the response rate for the ALXN2050 120 mg bid group is 45%, with a total of 67 evaluable participants, the study has approximately 80% power to detect the increasing trend in the proportions of responders using the Cochran Armitage test at a 2-sided type I error rate of 0.1.

Assuming approximately 5% non-evaluability, the study is planned to enroll 70 participants in total. The sample size calculations were performed in PASS 2020.

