5.3.4. Supplementary Analysis

The supplementary analysis on the primary endpoint will be performed based on the PPS using the Barnard's unconditional exact test. The purpose of this supplementary analysis is to provide additional insights for the primary efficacy result in a more compliant subgroup of the study population.

In addition, a logistic regression model will be established with the primary endpoint as the dependent variable and the study arm and baseline MG-ADL total score as covariates using the FAS. The purpose of this supplementary analysis is to provide additional insights for the impact of baseline disease characteristics to the primary analysis.

The following statistics will be presented:

- Adjusted response rate per treatment group
- 90% CI
- Adjusted odds ratio (OR; 180 mg bid versus placebo, 120 mg bid versus placebo, and 180 mg bid versus 120 mg bid) and 90% CI of OR
- P-value

| Endpoint | Analysis | Population | Method | Missing Data/Intercurrent Event Handling |
|---|---------------|------------|--|--|
| Proportion of participants with an MG-ADL total score reduction of ≥ 2 points from the Baseline in any 4 consecutive weeks during the first 8 weeks and who did not receive rescue therapy | Primary | FAS | 2-sided Barnard's unconditional exact test; 2-sided 90% CIs using Chan and Zhang method (Chan, 1999) for difference in proportions | Participants who discontinued early without achieving an MG-ADL total score reduction of ≥ 2 points from the Baseline in any 4 consecutive weeks during the first 8 weeks, will be considered as nonresponders. Participants who received rescue therapy anytime during the first 8 weeks will be considered as nonresponders. |
| | Secondary | FAS | 2-sided Cochran-Armitage test for trend; 2-sided 90% CI using the Clopper-Pearson method for proportions | |
| | Supplementary | PPS | 2-sided Barnard's unconditional exact test; 2-sided 90% CIs using Chan and Zhang method (Chan, 1999) for difference in proportions | |
| | Supplementary | PPS | 2-sided Cochran-Armitage test for trend; 2-sided 90% CI using the Clopper-Pearson method for proportions | |
| | Supplementary | FAS | Logistic regression with the primary endpoint as the dependent variable and the study arm and baseline MG-ADL total score as covariates | |

| Table 1: | Summary of Primary Endpoint |
|----------|-----------------------------|
|----------|-----------------------------|

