1.2. Changes From Analyses Specified in the Previous Version of the SAP

- Primary endpoint: primary endpoint analyses will be performed as described in the SAP Amendment Version 1.0 Section 5.3.2. Sensitivity and supplementary analyses will not be performed.
- Secondary efficacy endpoints: only change from baseline in the QMG total score and change from baseline in the MG-ADL total score as described in the SAP Amendment Version 1.0 Section 5.4.1.1 and Section 5.4.1.3 (excluding the trend analysis to detect dose-response trend) will be performed. Descriptive summary of absolute and change from Primary Evaluation Period (PEP) baseline in MG-ADL and QMG total score will tabulate study visits through the entire study. Supplementary analyses will not be performed.
- PK/PD: PK parameter will not be reported as described in the SAP Amendment Version 1.0 Section 5.7.1.3. Population PK and exposure-response analysis will not be performed as described in the SAP Amendment Version 1.0 Section 5.7.3. All other PK/PD analyses will be performed.
- Biomarker: biomarker analysis will not be performed.
- Safety: All safety analyses will be performed as planned, as described in the SAP Amendment Version 1.0 Section 5.6 with all data collected until the end of study.
- No exploratory endpoint analyses will be performed.
- All other analyses (e.g., demographic, baseline disease characteristics, MG/non-MG medications/therapies, protocol deviation, etc), if not mentioned above, will be performed as planned.

Study exposure and adverse event data summaries will include the following two sets of analyses: (1) summary of the PEP data by Group 1, 2, 3; (2) summary of the ALXN2050 Treated Period data by Group 1, 2, 3a, 3b. Per-protocol Set and Re-randomized Set will be removed.

Medication summaries by treatment group and overall using the number and percentage of participants will be presented by WHO-DRUG Anatomical Therapeutic Chemical Level 3 class code and by WHO-DRUG generic name.

All planned listings other than the ones for exploratory biomarker endpoints will be produced.

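### Does the Cochran-Armitage trend test need prespecified dose scores so that the 120 mg arm counts?

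*SAP*

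**What the plan says.** The trend across placebo, 120 mg and 180 mg is the secondary hypothesis (Protocol 9.1.2, SAP 2.2). The null is equal proportions in all three arms. The alternative is a non-decreasing order with at least one strict step.

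The test is named in five places, none of which gives group scores:

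- SAP 5.3.2.2: the trend "in the primary endpoint will be presented, along with the p-value using the Cochran-Armitage test".
- SAP Table 1: "2-sided Cochran-Armitage test for trend; 2-sided 90% CI using the Clopper-Pearson method for proportions".
- SAP 3: "approximately 80% power to detect the increasing trend in the proportions of responders using the Cochran Armitage test", at a two-sided level of 0.1.
- Protocol 9.2: "the study has approximately 80% power to detect the increasing trend in the proportions of responders, using Cochran Armitage test".
- Protocol 9.4.6.1.2: the trend "in the primary endpoint will be presented along with the p-value using Cochran Armitage test".

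SAP 1 places the table, figure and listing specifications in a separate data presentation plan, which is not among the documents reviewed. The addendum for the final report (its section 1.2) states that "primary endpoint analyses will be performed as described in the SAP Amendment Version 1.0 Section 5.3.2", so the trend test survives. The same section drops the sensitivity and supplementary analyses of this endpoint and the trend tests on the QMG and MG-ADL change scores.

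**The concern.** A Cochran-Armitage statistic is not fully defined until each arm has a score, and here the choice matters more than usual. Placebo and 180 mg are planned at equal size, so equally spaced scores put the mean score exactly on the 120 mg arm. That arm then has no weight in the numerator and enters only through the pooled response rate in the variance.

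Two consequences look bad. The p-value barely reacts to the 120 mg data, although the hypothesis is worded for three arms and one aim of the study is to choose a dosage. The small reaction that remains can also go the wrong way, since power is highest when 120 mg fails. A reader could take a small trend p-value as support for a dose ordering that the 120 mg participants did not supply. The apparent remedy is cheap: fix the scores at 0, 120 and 180 and restate the power.

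**Working it through.** **Inputs (SAP 3, same in Protocol 9.2).** Evaluable n: placebo 27, 120 mg 13, 180 mg 27. Response rates: 25%, 45% and 25% + 35% = 60%. Two-sided level 0.10, critical value 1.645.

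**Formula.** With scores s, the mean score is s̄ = Σ n·s / Σ n and the numerator is U = Σ x·(s − s̄), where x is the number of responders. The null variance is p̄(1 − p̄)·Σ n(s − s̄)², with p̄ the pooled rate, and Z = U/√variance.

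**1. The plan's own power figure, equal spacing (0, 1, 2).**

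- s̄ = (0·27 + 1·13 + 2·27)/67 = 1, so the centred scores are −1, 0, +1 and Σ n(s − s̄)² = 54.
- p̄ = (6.75 + 5.85 + 16.2)/67 = 0.4299; null variance = 0.4299 × 0.5701 × 54 = 13.23, SD 3.638.
- Mean of U = 27 × (0.60 − 0.25) = 9.45.
- Variance of U under the alternative = 27(0.25 × 0.75) + 27(0.60 × 0.40) = 11.54, SD 3.397.
- Power = Φ[(9.45 − 1.645 × 3.638)/3.397] = 0.846. With a continuity correction of half a step it is 0.809. Full enumeration without correction gives 0.851.

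**2. The same for scores 0, 120, 180.** Centred scores are −95.8, +24.2, +84.2. Power is 0.847 by the normal approximation and 0.846 by enumeration. Continuity corrections of 30 to 60 mg bring it to between 0.82 and 0.80. The stated figure of about 80% therefore fits either scoring, and neither contradicts it.

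**3. How far the 120 mg arm moves the result** (enumeration, no correction, placebo 25% and 180 mg 60%):

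| 120 mg response rate | Power, equal spacing | Power, scores 0/120/180 |
|---|---|---|
| 5% | 0.874 | 0.752 |
| 25% | 0.865 | 0.802 |
| 45% (planned) | 0.851 | 0.846 |
| 60% | 0.840 | 0.877 |
| 90% | 0.828 | 0.926 |

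Example p-values as the 120 mg count goes from 0 to 13 of 13:

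- 7/27 placebo and 16/27 on 180 mg: 0.010 to 0.014 with equal spacing; 0.033 falling to 0.003 with dose scores.
- 9/27 and 15/27: 0.089 at 0/13 and 0.101 at 6/13 with equal spacing; 0.212 and 0.101 with dose scores.

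At 25% against 60%, the 120 mg count can change the trend decision in 6.5% of placebo and 180 mg outcomes with equal spacing and in 19.9% with dose scores. The correlation of the trend Z with the two-arm Z at the planned rates is 0.999 and 0.991 respectively.

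**4. What the stated alternative requires.** If p1 ≤ p2 ≤ p3, at least one strict step exists exactly when p3 > p1. A statistic built on 180 mg minus placebo therefore tests that alternative directly. It does not test the ordering itself, and neither scoring makes it do so.

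**5. What dose scores would cost.** Take placebo 25%, 120 mg 75% and 180 mg 25%, so that there is no 180 mg effect and no monotone order. The chance of a significant result in the increasing direction is 0.040 with equal spacing and 0.102 with dose scores.

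**The case for a change.** The strongest case for a change is that the secondary hypothesis has an undefined statistic, and that two permissible definitions respond differently to the 120 mg data. Equal spacing can even move the p-value the wrong way, as the 9/27 and 15/27 example shows. The addendum sharpens this. With the logistic regression, the trend tests on the change scores and the exposure-response analysis all dropped, this is the only planned dose-trend test left for the final report. A definition that affects inference belongs in the SAP, whatever a programming document may say.

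The omission stands, and so does the near-equivalence to 180 mg versus placebo if the scores were equally spaced. It is not an artefact of exactly equal arms either: at 28/13/26 the 120 mg weight is only +0.03.

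The case for dose scores does not stand. They leave the statistic correlated at 0.991 with the two-arm comparison, and 0/13 responders on 120 mg still gives p = 0.033. They also make the misreading that is feared more likely under a non-monotone pattern. Milligram spacing has no special claim: Protocol 4.3 reports exposure rising more than in proportion to dose at steady state, and more than 90% inhibition of alternative pathway activity already at 120 mg.

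**Conclusion.** No change is called for. The scores are missing from the text, but this is a detail that the analyst must settle to run the test and can state when reporting it; the data presentation plan may already hold it. Between the two obvious choices there is a fair trade-off, with power at the planned rates differing by 0.851 − 0.846 = 0.005. The 120 mg arm's zero weight under equal spacing limits what the p-value can say about 120 mg, but the test remains valid for the hypothesis as written.

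Little rests on this p-value. Protocol 9 calls all results exploratory, Protocol 9.4.6.3 plans no multiplicity adjustment, and no stated decision depends on the trend. The 120 mg arm is judged from its differences against placebo and against 180 mg, with 90% confidence intervals, in the same SAP section, and the addendum keeps them. The addendum also records that the study was terminated for lack of efficacy relative to placebo at Week 8. Scores can therefore no longer be prespecified, and a misleadingly favourable trend has little practical weight.

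The figures assume the planned 27/13/27 evaluable participants and the uncorrected pooled-variance statistic, except where a continuity correction is stated. The zero weight holds only if the scores are equally spaced, which the documents do not say.

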5.3.3. Sensitivity Analysis

To assess the robustness of the main analysis of this endpoint to missing data during the PEP, the following sensitivity analysis will also be performed:

For participants with completely missing (eg, all items are missing) or partially missing MG-ADL assessments (eg, certain items are missing) at any visit from Weeks 1 through 8, a total score will be derived after imputing the missing items. Missing items will be imputed by taking average of the most recent assessment of the particular items before and after the partially missing assessment if both assessments are present within the PEP. If only the assessment prior to the partially missing assessment is available, last observation carried forward approach will be used.

Once the imputed dataset is produced, the primary endpoint will be analyzed with imputed data using the same method as described in Section 5.3.2.1 and Section 5.3.2.2.

5.3.4. Supplementary Analysis

The supplementary analysis on the primary endpoint will be performed based on the PPS using the Barnard's unconditional exact test. The purpose of this supplementary analysis is to provide additional insights for the primary efficacy result in a more compliant subgroup of the study population.

In addition, a logistic regression model will be established with the primary endpoint as the dependent variable and the study arm and baseline MG-ADL total score as covariates using the FAS. The purpose of this supplementary analysis is to provide additional insights for the impact of baseline disease characteristics to the primary analysis.

The following statistics will be presented:

- Adjusted response rate per treatment group
- 90% CI
- Adjusted odds ratio (OR; 180 mg bid versus placebo, 120 mg bid versus placebo, and 180 mg bid versus 120 mg bid) and 90% CI of OR
- P-value

| Endpoint | Analysis | Population | Method | Missing Data/Intercurrent Event Handling |
|---|---------------|------------|--|--|
| Proportion of participants with an MG-ADL total score reduction of ≥ 2 points from the Baseline in any 4 consecutive weeks during the first 8 weeks and who did not receive rescue therapy | Primary | FAS | 2-sided Barnard's unconditional exact test; 2-sided 90% CIs using Chan and Zhang method (Chan, 1999) for difference in proportions | Participants who discontinued early without achieving an MG-ADL total score reduction of ≥ 2 points from the Baseline in any 4 consecutive weeks during the first 8 weeks, will be considered as nonresponders. Participants who received rescue therapy anytime during the first 8 weeks will be considered as nonresponders. |
| | Secondary | FAS | 2-sided Cochran-Armitage test for trend; 2-sided 90% CI using the Clopper-Pearson method for proportions | |
| | Supplementary | PPS | 2-sided Barnard's unconditional exact test; 2-sided 90% CIs using Chan and Zhang method (Chan, 1999) for difference in proportions | |
| | Supplementary | PPS | 2-sided Cochran-Armitage test for trend; 2-sided 90% CI using the Clopper-Pearson method for proportions | |
| | Supplementary | FAS | Logistic regression with the primary endpoint as the dependent variable and the study arm and baseline MG-ADL total score as covariates | |

| Table 1: | Summary of Primary Endpoint |
|----------|-----------------------------|
|----------|-----------------------------|

| Endpoint | Analysis | Population | Method | Missing Data/Intercurrent Event Handling |
|----------|----------------------------|------------|--|--|
| | Primary Sensitivity 1 | FAS | 2-sided Barnard's unconditional exact test; 2-sided 90% CIs using Chan and Zhang method (Chan, 1999) for difference in proportions | LOCF for missing data after treatment discontinuation up to Week 8. Missing data during study |
| | Secondary Sensitivity 1 | FAS | 2-sided Cochran-Armitage test for trend; 2-sided 90% CI using the Clopper-Pearson method for proportions | treatment will be imputed by taking average of the most recent assessment before and after the missing assessment. |

Table 1:Summary of Primary Endpoint

Abbreviations: CI = confidence interval; FAS = Full Analysis Set; LOCF = last observation carried forward; MG-ADL = Myasthenia Gravis Activities of Daily Living; PPS = Per Protocol Set

